Alloclassic® Variall® Cup Ceramic Bearing System in Total Hip Arthroplasty

A multi-center, prospective, non-controlled post market surveillance study

PROTOCOL No. CME2014-03H

NCT NUMBER: NCT03672370

PROTOCOL VERSION:
2014-09 - REV. 01

STUDY SPONSOR

**ZIMMER GMBH
[name]
[name]
SWITZERLAND**

Title:	Alloclassic® Variall® Ceramic Bearing System in Total Hip Arthroplasty A multicenter, prospective, non-controlled post market surveillance study
Sponsor:	Zimmer GmbH
Objectives:	
The objectives of this study are to obtain survival and outcomes data on the Alloclassic® Variall® Cup in combination with the BIOLOX® delta Taper Liner when used in primary total hip arthroplasty. This will be done by analysis of standard scoring systems, radiographs and adverse event records. Data will be used to monitor pain, function and survivorship, and to confirm the safety and performance of the Alloclassic® Variall® Cup. Evaluation of squeaking and ceramic fracture rate will be an additional objective.
 
Safety will be evaluated by monitoring the frequency and incidence of adverse events.
 
Performance will be based on the implant survival, the overall pain and functional performances, subject quality-of-life and radiographic parameters of study subjects who received the Alloclassic® Variall® Cup. Pain and functional performance will be measured using the Harris Hip Score, survivorship will be based on removal or intended removal of the device. Subject quality-of-life will be determined by evaluation of the EQ-5D and the Oxford Hip Score, and radiographic parameters by analysis of x-rays.

Indication/ Target Population:	Patients, suffering from severe hip pain and disability requiring total hip arthroplasty, who meet the inclusion/ exclusion criteria.
Study Design:	Multicenter, prospective, non-controlled
Clinical Phase:	Post-market
Number of Subjects:	A total of 100 patients will be enrolled in this study
Length of Study:	12 years (2 year enrollment plus 10 years follow-up): follow-up visits at 3 months, 1, 2, 3, 5, 7, and 10 years post-operatively.
Study Device:	
Alloclassic® Variall® Cup in combination with:
 
Ceramic-on-Ceramic Articulation: BIOLOX® delta Taper Liner and BIOLOX® delta Femoral Head
 
Femoral Component: Avenir® uncemented Stem or Alloclassic® Variall® Stem

Comparator Device/ Procedure:	None

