Clinical Assessments:	Evaluations will be made using the Harris Hip Score, Oxford Hip Score, EQ-5D and radiographic evaluation.
Safety Assessments:	Safety will be assessed by appropriate recording and reporting of adverse events throughout the study. All system components are CE marked and commercially available
Statistical analysis:	Data collected will be summarized and reported to each participating Investigator. Statistical analysis is conducted by Zimmer or its designee.

General Statistical Method:

The assessment of efficacy for subjects receiving the total hip replacement system will be determined using the overall pain score and functional performance. Clinical success will be defined as a modified Harris Hip score of > 80 that included a rating of 'mild', or 'no pain'; a failure will be defined as a modified Harris Hip score < 80. Any study hip that required a subsequent surgical intervention where a stem head, cup, or liner was removed, or where a removal was planned, was considered a failure regardless of the Harris Hip score. Success rates will be expressed as percentages and primary summary results will be presented in tables which will contain the number and percentage of patients classified as a clinical success for the treatment group.

The assessment of safety will be evaluated by monitoring the frequency and incidence of adverse device effects in investigational subjects. As part of the safety profile, a survival analysis will be done.

Additionally, there are measures of interest which will be used to assess the investigational device such as radiographic success, all components included in the assessment of radiologic success, the EQ-5D, Oxford Hip Score, concomitant medication usage, and incidence of adverse events.

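### Does the clinical success percentage need a stated denominator and visit, so that missing Harris scores are not read as clinical decline?

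*Combined protocol and SAP*

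**What the plan says.** All of this is in the synopsis.

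- **Number of Subjects:** "A total of 100 patients will be enrolled in this study".
- **Length of Study:** 12 years in all, with "follow-up visits at 3 months, 1, 2, 3, 5, 7, and 10 years post-operatively". That is seven visits.
- **General Statistical Method, success:** "Clinical success will be defined as a modified Harris Hip score of > 80", together with a pain rating in one of the two lowest categories.
- **General Statistical Method, failure:** "a failure will be defined as a modified Harris Hip score < 80". A hip with a component removed, or with a removal planned, "was considered a failure regardless of the Harris Hip score".
- **General Statistical Method, population and reporting:** the section opens with "The assessment of efficacy for subjects receiving the total hip replacement system", and its main tables are to give "the number and percentage of patients classified as a clinical success for the treatment group".

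The text does not say at which visit or visits success is tabulated, who forms the denominator, or how a patient without a score is counted. It gives no hypothesis, target rate or expected follow-up for this endpoint. A survival analysis is planned separately, as part of the safety profile.

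**The concern.** The two classes do not cover everyone. A patient who has died, withdrawn or missed a visit, with no removal done or planned, has no score and is neither a success nor a failure. This holds whatever the pain categories are, and whether or not the inequalities include 80.

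The wording about the treatment group and about subjects receiving the system can be read as putting all treated patients in the denominator. Each unscored patient would then lower the percentage without having failed. Over 10 years the rate would slide as follow-up thins, even if no scored hip got worse. This is the plan's main efficacy summary, and there is no control arm with the same attrition to compare it with, so a reader could take loss to follow-up for loss of function. An analyst could also choose the denominator after seeing the data.

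**Working it through.** There is no figure in the plan to reproduce: it gives no success rate, follow-up rate or precision target.

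**Inputs.** N = 100 comes from Number of Subjects; that all 100 enrolled are treated is an assumption. Also assumed are p (success proportion), m (patients with no score and no removal or planned removal) and R (hips removed or with removal planned).

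**1. All treated as denominator, R = 0.** Successes S = p × (100 − m). The all-treated rate is S/100, and the gap from p is p × m percentage points. The highest rate the data allow, if every unknown is a success, is (S + m)/100.

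| p | m | S | All-treated rate | Gap (points) | Highest possible |
|---|---|---|---|---|---|
| 0.80 | 5 | 76 | 76% | 4 | 81% |
| 0.80 | 10 | 72 | 72% | 8 | 82% |
| 0.80 | 20 | 64 | 64% | 16 | 84% |
| 0.80 | 30 | 56 | 56% | 24 | 86% |
| 0.70 | 30 | 49 | 49% | 21 | 79% |
| 0.90 | 30 | 63 | 63% | 27 | 93% |

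For scale, the 95% half-width for 80% in 100 patients is 1.96 × √(0.8 × 0.2/100) = 7.84 points. With m = 0 the gap is zero.

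**2. Scored-or-removed as denominator.** This rate is not immune either. Removals stay in as failures while unscored, unrevised patients leave. Take R = 5 and 90% success among scored hips, so that 95 hips are unremoved:

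- none missing: 0.9 × 95 = 85.5 expected successes; 85.5/(95 + 5) = 85.5%
- 28 missing (about 30%): 0.9 × 67 = 60.3; 60.3/(67 + 5) = 83.8%
- 48 missing (about 50%): 0.9 × 47 = 42.3; 42.3/(47 + 5) = 81.3%

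Only a scored-only rate is free of the mechanical fall (90% throughout here). It leaves the removals out and relies on the unscored resembling the scored.

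**3. Can a reader tell which denominator was used?** Denominator = number ÷ percentage. For p = 0.80 and m = 30, 56 successes printed as 56% give 56/0.56 = 100, and printed as 80% give 56/0.80 = 70. Rounding to a whole percent does not blur this: 56/0.805 to 56/0.795 is 69.6 to 70.4, which contains only 70. Set against the 100 enrolled, the second table shows 30 patients unaccounted for.

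**The case for a change.** The best case for acting is that this is the main efficacy table of a study meant to monitor function over time. There is no comparator, so the absolute percentage carries the message. At plausible attrition the choice of denominator moves it by more than its sampling error. Stating the denominator and visit would take a few sentences, and would remove a choice that could otherwise be made after the data are seen. The survival analysis concerns removals and cannot stand in for a Harris-based rate.

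Part of this stands. The text shown does leave unscored, unrevised hips unclassified and does not fix the denominator in advance. Recovering the denominator from the table also does not show why patients are missing.

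The consequence is weaker than it looks. The all-treated reading is not compelled: with no comparator, the treatment group may simply mean the only group, and the opening words of the section name a population, not a divisor. Seven scheduled visits in a monitoring study point naturally to a table by visit. The planned counts expose whichever denominator is used. Choosing one in advance would not recover the unknown outcomes, and of the three denominators only the scored-only rate escapes the fall, at the price of leaving the removals out. No test, target or stated decision depends on the percentage.

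**Conclusion.** No change to the plan is called for. The observation is accurate: in this synopsis-level text, a patient with no score and no removal or planned removal is in neither class, and the tabulation visit and denominator are not stated. This is missing detail in a descriptive, non-controlled study, of a kind analysts ordinarily fill by tabulating each visit among patients with a known status and showing the counts. The feared misreading needs the all-treated denominator, and the number and percentage already promised would reveal it.

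On that reading the fall is p × m points: 4 points for 5 missing and 24 for 30 missing at 80% success. On a scored-or-removed denominator it is about 2 points (85.5% to 83.8%) with 28 missing, 5 removals and 90% success among scored hips. These sizes rest wholly on assumed success, removal and missingness rates. The survival analysis does not use this success percentage and is unaffected.
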